Data collection will be conducted at the Northampton VA Medical Center and the West Haven VA Medical Center. Veterans will complete baseline evaluations, and then be given a user ID and instructions to log-on to a study website at home to receive their randomization assignment. Only those who do so will continue in the study and be asked to complete the telephone-delivered assessments on weeks 4, 12, and 24. This randomization after logging in restricts participation to people who demonstrate some motivation and ability to access a website.

Sequence of procedures for the clinical trial:

- Potentially eligible Veterans scheduled for a Compensation examination are identified by reviewing Compensation clinic schedules and charts.
- Potentially eligible Veteran receives letter explaining that a study recruitment telephone call will be coming, thus allowing the Veteran to opt out of receiving it (see Appendix). Veterans can also opt out by calling a toll-free phone provided in the letter.
- Telephone call inviting participation. The Research Assistant calls and asks the Veteran questions to determine eligibility. Following a script (see Appendix), the Research Assistant describes the study to the Veteran and schedules an appointment for informed consent and data collection. Appointments will be scheduled before a Veteran's planned Compensation examination and up to 3 months after the exam. Veterans vary in how able they are to schedule appointments immediately before or after Compensation examinations. Flexible scheduling balances feasibility and experimental rigor.
- Informed consent and baseline data collection by Research Assistant.
- The Research Assistant gives the Veteran a user ID and password to log on to the study Website.
- Veteran goes home, logs onto the website, and receives directions to log-on to either the Benefits Counseling or Control websites (i.e. the Veteran is randomized).
- Veteran is called by the study therapist within two days of logging on and is counseled with the assigned treatment. If the Veteran has not logged on for randomization within a week, then the therapist will call and encourage the Veteran to log-on for randomization and continuation in the study. If after one more week the Veteran has not been randomized, that participant will be discontinued from the study.
- Assessments by phone at weeks 4, 12, 24 (only of randomized Veterans).

B. Remotely-Delivered Benefits Counseling

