1. Integration of Website Use and Therapist Phone Calls:

- a. Purposes of Phone Calls:* The purpose of the Benefits Counseling phone calls is to complement the web-based modules and to support the Veteran in applying the website content to his/her particular situation.
- b. Introduction:* The therapist explains that his/her role is to help the Veteran get as much as possible out of the Benefits Counseling website. The therapist plans the dates and times for phone calls and provides the Veteran with a phone number to call him/her for rescheduling or brief questions.
- c. Timing and Content of Session Calls:* The therapist tries to schedule calls soon after the Veteran has completed each of the first two modules. At each of the calls, the therapist makes general inquiries about the Veteran's experience using the site, the information covered, and any follow-up the Veteran plans. Based on these responses, the therapist

will follow-up with questions about the content of the module just completed (domains described below).

d. Timing and Content of Session-Three Call: Therapists will instruct Veterans to complete Module Three after receiving their service-connection decision and to call after completing it. If the Veteran has not called by week 12, the therapist will call the Veteran to determine the status of the C&P claim, and module completion. If the C&P decision has not been received, the therapist will call again at 16 and 20 weeks to review the decision and module, if the Veteran hasn't called first.

e. Overall Call Limit: Therapists will limit calls to no more than 30 minutes each, and no more than three therapy calls per Veteran; calls lasting fewer than five minutes (e.g. for scheduling or brief questions) will not count towards the three call limit.

2. Website

a. The VACHS IRB reviewed the website's content as part of protocol MR0031, IRB #01389, for preliminary use by Veterans. Screenshots of the website are attached as an Appendix.

The website can also be accessed by

Going to vabenefitseducation.org
 Entering username [name]
 Password bluefish
 Selecting go to cloned interview.

b. The Goals and Content of the Three Modules: In keeping with published literature and our pilot experience, we kept the intervention modules brief (about 20-30 minutes each).

Module	Module's Goals	Session Content in Brief

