We planned our precision analysis around an effect size of 0.4 because (a) the effect size in our RCT of face-to-face Benefits Counseling was $\delta=.69$ and (b) an effect size of 0.4 is clinically meaningful. An additional 2 days worked reflects earning a substantial amount of additional money for people with limited incomes, in addition to other benefits associated with working.

D. Experimental Participants

1. Inclusion and Exclusion Criteria

a. *Inclusion Criteria*: All enrolled participants will have difficulty working as evidenced by a “Yes” response to any sub-part of the question below (from the SF-36, [51]): “During the past 4 weeks, have you had any of the following problems with your work or other regular daily activities as a result of any emotional problems (such as feeling depressed or anxious): (a) Cut down on the amount of time you spent on work or other activities? (b) Accomplished less than you would like? (c) Didn’t do work or other activities as carefully as usual?”

Participants will also meet the following inclusion criteria: (i) A Compensation and Pension evaluation by a psychiatrist or psychologist is scheduled; (ii) Does not have a service-connected physical disability rated over 30%; (iii) Is not service-connected for a psychiatric condition (0% service-connection is allowed, as Veterans with 0% service-connection have not received any benefit payments); (iv) Age 18-65; (v) Reports access to an internet-connected computer/tablet and a working telephone; (vi) Reports working no more than 24 hours per week for pay over the preceding 4 weeks; (vii) Self-reported ability to participate psychologically and physically, able to give informed consent and complete assessments; (viii) Reports being able to read (this is necessary for understanding the website); (ix) Expressed interest in sampling whatever website is provided.

b. *Exclusion Criteria*: (i) Already receiving service-connection, SSI or SSDI; (ii) Has a conservator.

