The general potential *mediators* of treatment response will include ratings of importance/confidence in ability to work, work-benefits attitudes (attitudes about one's personal situation, understanding of work-benefits relationship), service-connection award, and number of weeks engaged in any mental health and/or substance abuse treatment.

5. Evaluation of Process Measures: The Likert-scaled therapy process ratings and other measures reflecting single values (e.g. number of times logging into the study website) will be compared between groups using parametric or non-parametric group comparisons. Only the Benefits

Counseling group will have ratings of audiotaped therapy sessions and these will be tabulated for descriptive statistics.

6. Evaluation of Factors Associated with Effects of Study Treatments on Working (Moderators)

To determine what factors are associated with response to counseling, potential predictor variables will be serially entered into the primary outcome analyses as separate covariates, and as terms interacting with group-assignment. To avoid finding significant associations by chance, potential predictors will be screened for their intercorrelations with each other and redundant measures (e.g., $r > .7$; $R^2 \geq .6$; $VIF \geq 2.5$) will be pared or combined. Potential predictor variables include:

- Demographic variables (age, race, gender),
- Conditions that Make Working More Difficult: Substance use severity, baseline PTSD severity as measured by the PCL-5, overall psychological symptomatology as measured by the BSI, depression as measured by the BSI.
- Attitudes Toward Seeking Professional Psychological Help Scale-Short Form (two domains---openness to seeking treatment for emotional problems and value of seeking treatment).
- Veterans' rated reasons for seeking compensation as described by the Disability Application Appraisal and Inventory [28]: we hypothesize that Veterans who rate themselves higher in having applied for financial gain will be more likely to work in response to Benefits Counseling.

7. Evaluation of factors associated with progress through different steps of study participation

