Justification for recruitment via mailed letter: The proposed letter recruitment strategy, which was used in several of [name] other approved studies including two SBIRT studies (projects which deliver SBIRT to Veterans applying for disability for painful musculoskeletal conditions or PTSD) and the QUERI study (a multi-site study of the Compensation and Pension process directed by [name]), was effective. The main reason for recruitment by letter is that it would not be feasible to recruit Veterans at the time they come for their Compensation examination because Veterans may not have time to consider study participation when they are already at their Compensation examinations. Veterans at their Compensation and Pension evaluations may be nervous and rushed. They may be accompanied by other people who cannot or will not wait while the Veteran participates in an unplanned study. Additionally, assessments are designed to be collected before the Compensation examination.

A second mode of recruitment will involve having C&P clinic staff (but not the C&P examiner) give potentially eligible Veterans a study brochure and ask them if they are willing to discuss study participation with a member of the study staff. If they are, a member of the staff will contact them at the C&P office, if feasible, or by phone.

2. Consent: Voluntary informed consent will be obtained from all Veterans prior to participation. Consent will be obtained by one of the investigators or his/her designee after the research procedures and risks associated with participation have been explained to the candidate. A signed copy of the consent form will be provided to all potential Veterans.

Participants will be asked several questions to be certain they understand the risks associated with study participation. Only participants who correctly answer all the questions (with a second chance to answer questions if incorrectly answered the first time) will be enrolled. The questions will be the following:

a. What topics will you be asked about?

Answer should mention working.

b. Is it possible that someone will learn that you were at the study website?

The correct answer is "Yes."

c. Can you drop out of this study whenever you want? Yes.

B. Risks and Discomforts

Risks associated with participation in the study include risks associated with:

1. Completing questionnaires: Administration of study instruments may be boring, frustrating, or upsetting.

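### A claim decided before log-on makes the service-connection award a pre-randomization fact, which cannot be a mediator, and no eligibility criterion requires the claim to be undecided

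*Combined protocol and SAP*

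**What the plan says.** All references are to the combined protocol and SAP.

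- **Research plan, A. Study Design Overview.** The appointment for consent and baseline may be before the Veteran's "planned Compensation examination and up to 3 months after the exam". The stated reason is that flexible scheduling balances feasibility against rigor. Randomization happens later, when the Veteran logs on from home. The therapist prompts after one week. "If after one more week the Veteran has not been randomized", participation ends.
- **D.1 Inclusion and Exclusion Criteria.** Inclusion (i) reads "A Compensation and Pension evaluation by a psychiatrist or psychologist is scheduled". Inclusion (iii) reads "Is not service-connected for a psychiatric condition (0% service-connection is allowed", on the ground that such Veterans have had no payments. Exclusion (i) bars those already receiving service-connection, SSI or SSDI. No criterion mentions a pending, decided or denied claim.
- **B.1.d, Session-Three Call.** Therapists tell Veterans to "complete Module Three after receiving their service-connection decision and to call after completing it". Failing such a call, the therapist checks on the claim at week 12, and calls again at weeks 16 and 20 if there is still no decision.
- **Data Analysis, section 4.** The potential mediators include "service-connection award, and number of weeks engaged in any mental health" or substance abuse treatment. Each is to be related to group assignment and to the slope of hours worked.
- **Human Subjects, A.1 Recruitment.** In justifying the recruitment letter, the text says that "assessments are designed to be collected before the Compensation examination".

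**The concern.** The trial is described as one of Veterans who are applying for service-connection, and Module Three is built to follow the decision. The entry rules fix the timing of baseline relative to the examination, but not relative to the decision. For late entrants the claim may already be settled, and then eligibility depends partly on how it was settled.

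What is at stake is the award as a mediator. A mediator has to be something that assignment could alter. An initial decision dated before log-on is a baseline characteristic. If such Veterans are pooled with the rest, the association between assignment and award is diluted. The association between award and hours worked then mixes prognosis at entry with events during follow-up. The partial correlation that controls for the award has the same problem.

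**Working it through.** **1. Latest randomization relative to the examination.** Inputs, from the Study Design Overview: 3 months, about 13 weeks, to baseline; then 1 + 1 weeks to log on. 13 + 2 = 15 weeks. The text therefore leaves room for a decision before randomization.

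**2. Who passes the criteria if the claim was decided before the screening visit.**

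| Decision on the psychiatric claim | Criterion that applies | Result |
|---|---|---|
| Awarded above 0% | Inclusion (iii), exclusion (i) | Cannot enter |
| Awarded at 0% | Inclusion (iii) allows it expressly | Can enter |
| Denied | None | Can enter |

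Two qualifications apply. Eligibility is checked at the telephone call and at the face-to-face visit, and no check is described at log-on, so a Veteran awarded between baseline and log-on stays in. Also, exclusion (i) taken literally sits badly with inclusion (ii), "Does not have a service-connected physical disability rated over 30" percent, which implies that smaller physical ratings are acceptable. That wording needs reconciling as well, but it does not alter the table for denials.

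**3. The three statements on timing.** The Study Design Overview allows baseline after the examination. Human Subjects A.1 says assessments are designed to come before it. Inclusion (i) requires an evaluation to be scheduled, which could mean still ahead at baseline, or merely scheduled when the telephone call is made. Under either reading it concerns the examination and not the decision.

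**4. Effect on the mediator analysis.** Let f be the share of randomized Veterans decided before log-on, and D the between-arm difference in award proportion among the undecided. Among those already decided, the expected difference is 0, because assignment came later. The pooled expected difference is (1 − f) × D + f × 0 = (1 − f)D.

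The documents give no value for f. The values below are assumptions to show scale only. The numbers left use the plan's 104 Veterans with at least one follow-up and assume the same f among them.

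| Assumed f | Decided before log-on, of 130 | Left for the award analysis, of 104 | Pooled difference |
|---|---|---|---|
| 0% | 0 | 104 | 1.00 D |
| 5% | 6.5 | 98.8 | 0.95 D |
| 10% | 13 | 93.6 | 0.90 D |
| 20% | 26 | 83.2 | 0.80 D |

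**5. The plan's own precision figure.** With 52 per arm and δ = 0.40, the standard error is √(2/52 + 0.40²/(4 × 52)) = √(0.03846 + 0.00077) = 0.198. The interval is 0.40 ± 1.96 × 0.198, or 0.012 to 0.788, which agrees with the stated (.01, .79). Allowing for the planned loss, 104/0.80 = 130 randomized, also as stated. The restriction proposed here removes no one from the primary analysis, so neither figure changes.

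**The case against.** The strongest reply is that the problem may hardly occur. No adjudication time is given, and the planned calls at weeks 12, 16 and 20 suggest that the investigators expected many decisions well after randomization. A share near zero is as compatible with the text as any other. This stands, and it is why no count of affected Veterans is claimed.

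The harm is also confined. The award appears only in the list in Data Analysis section 4, not in Hypotheses 2A or 2B, and the plan says that it is not powered for full mediation. This too stands.

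Three stronger readings are tempting, and the documents do not support them:

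- **That the primary comparison is biased.** Claim status at log-on precedes assignment, so randomization protects the comparison. Data Analysis section 3 also allows covariate adjustment if a baseline difference related to outcome is found, although claim status would have to be recorded for that to help.
- **That every awarded Veteran is shut out and every early-decided entrant was denied or rated 0%.** Awards of 0% are allowed, and an award made between baseline and log-on does not remove the Veteran.
- **That the intervention has no meaning after a denial.** Module One explains how work and benefits relate, Module Two concerns motivation and an action plan, and Module Three covers denial and appeal. A denied Veteran may still be pursuing benefits.

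Finally, the post-examination window is a reasoned feasibility choice. A rule excluding decided claims would cost recruits, and the documents give no consent rate from which to judge whether that is affordable.

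**Conclusion.** The concern holds in a limited form. The documents permit randomization up to about 15 weeks after the examination, do not require an undecided claim, and admit a Veteran already denied but not one awarded above 0% by screening. For any claim decided before log-on, the initial award decision cannot mediate the effect of assignment.

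The frequency is unknown. The expected dilution of the assignment–award association is the factor (1 − f), with f not given by the documents. This rests on defining the mediator as the initial decision on the index psychiatric claim; a later award on appeal would be a different, post-randomization variable. The primary analysis is not affected. This is an inexpensive correction to an exploratory analysis, together with a needed clarification of the entry text.

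**What to change.** 1. In Data Analysis section 4, restrict the service-connection-award mediator analysis to Veterans whose claim was undecided at randomization. The restriction uses a pre-randomization characteristic, so the arms remain comparable by design. Report in each arm how many were decided before log-on.
2. Take the decision date from the VBA extract. The service-use window under End of Study Measures, item 2, runs to 24 weeks after adjudication and so already needs this date; list it explicitly as an extracted item. The extract is preferable to therapist inquiry, because the decision-related call is described only for Benefits Counseling.
3. Reconcile the Study Design Overview, inclusion (i) and Human Subjects A.1 on when baseline may occur, and state whether an undecided claim is required for entry.

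The cost is a few lines of text and a somewhat smaller sample for one exploratory analysis. The intention-to-treat set stays as it is. Adding an eligibility restriction, or balancing the urn on baseline before versus after the examination, is a design option for the investigators and not a required correction.

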Remotely-Delivered Benefits Counseling for Service
Connection Applicants

NCT02677428

4/9/19

Project Description

1. Principal Investigator

[name]

2. Project Title

Remotely-Delivered Benefits Counseling for Service Connection Applicants

3. Purpose

The purpose of this study is to evaluate the utility of Remotely-Delivered Benefits Counseling in a 24-week clinical trial. This study will evaluate the effectiveness of Benefits Counseling on work and work-related outcomes with Veterans who are applying for service-connection. This study has the following specific aims and hypotheses:

Primary Aim 1: To estimate the effect of Remotely-Delivered Benefits Counseling on the slopes of paid work over time.

Hypothesis: The slopes of hours of paid work over time will differ between the control and Benefits Counseling groups, as evidenced by a significant, positive treatment-by-time interaction effect.

Exploratory Aim One: To estimate the effect of Remotely-Delivered Benefits Counseling on other outcomes.

Hypothesis: The slopes of hours of volunteer work; days attending school, days in vocational rehabilitation settings, days engaged in any one of the work-related activities; and income earned over time will differ between the control and Benefits Counseling groups.

Exploratory Aim Two: To conduct bivariate analyses of two of the components of mediation of Benefits Counseling's effects---correlation with the group assignment and with the outcome:

Hypothesis 2A: Assignment to Benefits Counseling (vs. control) will be associated with one or more of the following: (i) more positive changes in ratings of work's importance, (ii) greater decreases in beliefs that working and service connection are linked, and (iii) more positive changes in number of weeks attending any mental health or vocational counseling.

Hypothesis 2B: Individual slopes in hours worked over time will be associated with one or more of the potential mediators (i, ii, iii) as above in Hypothesis 2A.

4. Background

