Benefits Counseling was evaluated in an observational cohort study among Social Security recipients with psychiatric conditions who had expressed some interest in working [26]. Participants received an average of 8 hours of counseling. Remarkably, those beneficiaries who received this Benefits Counseling earned an average of \$1,256 more per year than matched controls. Subsequently, a large, randomized controlled trial of Benefits Counseling as part of a multi-component bundled intervention found a large and significant effect; 61 percent of Benefits Counseling participants were working at follow-up compared to only 41 percent of control participants [27]. Our group’s work extended these findings to Veterans applying for service-connection for psychiatric conditions. We developed a Veteran-specific manual based on published literature---primarily that of Robert Drake and colleagues [26] and Nina Sayer [28-30].

Vocational rehabilitation materials were developed with input from our VISN 1 MIRECC collaborators, primarily [name] and [name], and input from rehabilitation experts at VA Connecticut ([name], [name]). The material was discussed with Veterans, Veterans' Service Organizations, and Veterans Benefits Administration stakeholders. It was then pilot tested and further refined. We demonstrated Benefits Counseling's efficacy among Veterans in a randomized clinical trial published in *Psychiatric Services* [31]. The study utilized many methodologies that are in the proposed study -recruitment of Veterans applying for service-connection for a psychiatric condition, use of a timeline followback calendar to assess daily amount of work done, and assessment 4, 12, and 24 weeks after randomization. The main outcome analysis found that Benefits Counseling was associated with a significantly greater slope in days worked for pay than the control condition ($p=.01$). The effect size for this difference was 0.69 (standardized mean difference in slope estimates between the Benefits Counseling and control groups), a large effect for a behavioral intervention.

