- b. The VBA site with fact sheets about the different types of benefits available to Veterans. The topics covered in these fact sheets are: General Benefit Information, Veterans with Service-Connected Disabilities, Veterans with Limited Income, Education and Training for Veterans, Home Loans, Dependents and Survivors' Benefits, Burial and Memorial Benefits, and Insurance.
- c. The VBA websites for the local C&P office where issues pertaining to an individual Veteran's specific application are addressed. The site includes phone numbers to call with questions, e-mail contacts and directions to the VBA office.

3. Role of Therapists in Control Condition: The therapists in the control condition will differ from the Benefits Counseling therapist as shown in the table below

Control Therapist	Benefits Counseling Therapist
Initiate calls to Veterans at weeks 1 and 2	Initiate calls to Veteran at weeks 1 and 2 and around time of Module Three (or thereafter)
Up to three therapy calls of up to 30 minutes each	Up to three therapy calls of up to 30 minutes each
Convey information about Veterans Benefits	Convey information about Veterans Benefits AND vocational issues
Offer to elaborate on information on control websites	Inquiry about modules on Benefits Counseling website. Follow-up inquiries about domains covered on site.

Justification of Sample Size

We estimate that 190 Veterans will be enrolled and complete baseline assessments; 130 will log-in to the randomization site and be assigned to a treatment condition; 104 (52 per condition) will complete at least one follow-up assessment.

Precision Analysis

Consistent with the purpose of a pilot study, the sample size was selected to

estimate the standardized effect of treatment with reasonable precision, rather than to power for a statistically significant effect [50]; A **sample size of 52 per treatment condition** permits estimation of an expected standardized difference in slopes of hours worked between Benefits Counseling and control groups (e.g., (slopeBC-slopeCON)/SDslope) of $\delta=.40$ with a 95% confidence interval of (.01, .79). This effect would reflect an average 6% increase in baseline number of hours worked per month, or a total increase of 43% by month 6. Assuming an average baseline event rate of 40 hours/28 days and no change in the control group, this effect is equivalent to approximately 17 additional hours (approximately 2 days) of work per month by month 6.

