3. Evaluation of Treatment Effects: For baseline values potentially related to outcome, evaluation of comparability of the two treatment groups will be conducted using chi-square tests for categorical variables and t-tests for continuous variables. If an unexpected difference is found and is related to the outcome, the potentially significant confounding variable will be added to the primary outcome analysis as a covariate.

The principal strategy for assessing the efficacy of the study treatment will be random effects regression, which will be used to determine the differences in slopes of outcomes between Veterans assigned to Benefits Counseling compared to Control. The model will include covariates described in the Introduction Section, time measured in weeks, and the contrasts of Benefits Counseling versus Control. A linear effect of time on outcome variables is being hypothesized but ancillary analyses will be conducted to determine if the effect of Benefits Counseling treatment is better explained by a quadratic function (as described in the Introduction section of this grant). Models will be specified to accommodate the observed distributions of outcomes (e.g., Poisson, normal, Bernoulli) and theory, model estimates, and fit indices will inform the specification of effects as fixed or random, and the structure of the variance-covariance matrix.

Our principal data analyses will be conducted on all randomized Veterans. We will attempt to follow all participants who are randomized for assessments regardless of their retention in treatment. Intention-to-treat analyses will be supplemented by analyses to describe the consistency of findings across different definitions of the sample: e.g., module-completers and treatment completers. Measures of engagement in Benefits Counseling will also be tested for their association with outcomes (number of days using the website, modules completed, minutes on phone with Benefits Counselor).

4. Evaluation of Processes that Might Mediate Treatment Response: This study is not powered for full mediation analyses but will allow for bivariate analyses of the components of mediation. Bivariate analyses will be conducted of the relationship between the slope of each potential mediator and (1) group assignment and (2) slope of hours worked per week. The partial correlation of group assignment with the slope of hours worked per week will be calculated, controlling in turn for each potential mediator's slope.

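### Does leaving the model for paid hours open undermine the pilot's planned effect size of .40?

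*Combined protocol and SAP*

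**What the plan says.** The combined protocol and SAP, under Justification of Sample Size (Precision Analysis), says that the number of Veterans was chosen to "estimate the standardized effect of treatment with reasonable precision, rather than to power for a statistically significant effect". With 52 per arm it expects a difference in slopes of hours worked, divided by the SD of slopes, of .40 with a 95% interval of (.01, .79). That ratio is given only as an example, and the SD has no value. The effect is then put as "an average 6% increase in baseline number of hours worked per month, or a total increase of 43% by month 6". The conversion to hours rests on this premise: "Assuming an average baseline event rate of 40 hours/28 days and no change in the control group". It comes to about 17 extra hours a month by month 6.

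Under Data Analysis, item 3 (Evaluation of Treatment Effects), random effects regression is the principal method for comparing slopes. "A linear effect of time on outcome variables is being hypothesized", with a quadratic form as an ancillary analysis. On the model itself: "Models will be specified to accommodate the observed distributions of outcomes (e.g., Poisson, normal, Bernoulli"). The sentence goes on to say that theory, together with "model estimates, and fit indices will inform the specification of effects as fixed or random".

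The hypothesis for Primary Aim 1 is a difference in slopes "as evidenced by a significant, positive treatment-by-time interaction effect". The earlier face-to-face trial, described under Evidence of Benefits Counseling's Efficacy, reported that "Benefits Counseling was associated with a significantly greater slope in days worked for pay than the control condition", with an effect size of .69 computed on slope estimates.

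**The concern.** Three things look loose together.

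- **Growth.** Adding 6% of baseline for six months gives 36%, not 43%. The stated total needs compounding, so .40 appears to be an effect on a log-rate scale, although the text speaks of slopes of hours.
- **Distribution.** The analysis section does not commit hours of paid work to a log-link or a linear model.
- **Denominator.** The slope SD is undefined. If the time slope were treated as fixed, the model would supply no random-slope SD.

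The stated product of the pilot is this standardized effect, and its planned lower limit is only .01. If the scale were picked after seeing results, the estimate, its interval and the verdict on Primary Aim 1 could all move. The earlier .69 was for days rather than hours, so it does not settle the scale.

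**Working it through.** **Inputs from the Precision Analysis.** 52 per arm, d = .40, 6% a month, 43% by month 6, baseline 40 hours per 28 days, no change in controls, about 17 hours.

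**1. The interval.** SE = sqrt(2/52 + .40²/(4 × 52)) = sqrt(.03846 + .00077) = .198. Then .40 ± 1.96 × .198 = (.01, .79), as printed. The retention figures also agree: 130 × .80 = 104 = 2 × 52.

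**2. The growth figures.**

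| Reading of 6% a month | Total by month 6 | On 40 hours |
|---|---|---|
| Linear: 6 × .06 | 36% | 14.4 h |
| Discrete compounding: 1.06⁶ − 1 | 41.9% | 16.7 h |
| Log-rate slope: exp(6 × .06) − 1 | 43.3% | 17.3 h |

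The log-rate line reproduces both 43% and about 17 hours. Stating growth in percent and calling the 40 hours an event rate both fit that reading, and Poisson is the first distribution listed in the analysis section. The linear line is a different reading, not a correction.

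**3. The implied slope SD.** On the log-rate scale it is .06/.40 = .15 a month. On the hours scale it would be (17.3/6)/.40 = 7.2 hours a month. Normal slopes with that SD, starting from 40 hours, would put about 18% of controls below zero hours by month 6. That is a reason not to read the planning figures as slopes in hours. It does not show that they are wrong.

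**4. Would the random slope be dropped?** The spread of individual change by month 6 would be 6 × .15 = .90 log units, or 6 × 7.2 = 43 hours on a mean of 40. Fit indices would hardly miss that. In a null simulation under a normal model (300 trials per case, slope SD 7.2 hours), selection by fit index kept the random slope every time, with a type I error of 5%. In addition, Hypothesis 2B and Data Analysis item 4 both need each Veteran's slope. An SD of individual slope estimates can be computed without a random-slope term, and the earlier .69 was standardized on slope estimates.

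**5. The 17 hours as a difference in arm means.** If log-rate slopes have mean 0 in controls and SD .15, mean hours at month 6 are 40 × exp(.405) = 60.0 for controls and 40 × exp(.765) = 86.0 for Benefits Counseling, a difference of 26. But control hours then rise from 40 to 60, against the stated assumption of no change. The ratio is still 86.0/60.0 = 1.433. Holding the control mean at 40 at month 6 gives 40 × 1.433 = 57.3, a difference of 17.3 hours, which is the plan's figure.

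**6. How far the scale could matter.** Taking the log-rate effect as true and re-expressing it as slopes in hours gives standardized effects of .19 to .37 over 18 assumed combinations of baseline shape and cap on hours.

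- All the intervals cover zero, but at 52 per arm this happens for any d below about .388, where 1.96 × sqrt(2/52 + d²/208) equals d. The width hardly moves: .77 at d = .19 and .78 at d = .40.
- Simulated log-scale and hours-scale tests disagree on p < .05 in 11–29% of trials. Power at .40 is only about 53% (.40 × sqrt(26) − 1.96 = .08, and Φ(.08) = .53). Two valid tests with power near one half and a correlation of .7 to .9 disagree in 14–25% of trials anyway.
- With no effect, at least one of the two tests is significant in 6.2–7.9% of trials. That assumes the significant model is always the one reported.

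**The case for a change.** The strongest case is that a pilot whose product is an estimated effect size should fix the scale and denominator of that effect. The data analysis section itself says that defining the primary outcome in advance limits type I error, and an open model weakens that protection. With a planned lower limit of .01, even a small shift between scales can change whether zero is excluded. The remedy would be text only.

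Part of this stands. The plan does not name the distribution and link for hours, and it does not say which SD was meant. A stated choice would have been tidier.

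The rest is weaker. The criterion given for the model is the observed distribution of the outcome, not the treatment result. The sentence on fixed and random effects lists theory ahead of fit, says that these inform the choice, and speaks of effects in general rather than the time slope. Nothing in the plan allows both models to be run and the favorable one reported. The lowest hours-scale effects come from a model in which a Veteran with no hours at baseline can never start work, although moving such Veterans into work is an aim of the intervention.

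**Conclusion.** No printed figure is wrong. The interval follows from 52 per arm and d = .40, and 43% and 17 hours follow from a log-rate slope of .06 a month on a base of 40 hours. What is left is a gap in detail that analysts can fill sensibly: the planning figures point to a log-rate slope, and the analysis plan to random effects regression with person-level slopes.

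Tying the model to the observed distribution is a fair trade-off. A log-link model learns little or nothing about the slope from Veterans with no paid hours at any visit. A linear model keeps them but no longer matches the 43% and 17 hours. The number of such Veterans cannot be known in advance.

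The worst case found, always reporting whichever of two models is significant, adds about 1 to 3 points to a 5% error rate, and the plan does not provide for it. This conclusion assumes that 6% is a compounding rate, as the 43% requires, and that the time slope stays random, as the analyses of individual slopes imply. The grant's introduction, to which the plan refers for covariates and the quadratic form, is not in the document and could not be checked. No change to the plan follows.
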